Over 4 million US adults regularly smoke cigars, which causes multiple cancers, including oral, esophageal, pancreatic, laryngeal, and lung cancer. (NCI ,1998; Chang, 2015) Even smoking 1-2 cigars per day is associated with elevated cancer risk. Though cigarette consumption decreased 39% from 2000 to 2015, cigar consumption increased 85%. (Wang, 2016) Of the three major types of cigars—large cigars, little cigars, and cigarillos—little cigars and cigarillos (LCC) are the most commonly used in the US. (Delnevo, Giovenco, 2017; Delnevo, Hrywna, 2017) LCC use among adults has increased, in part, because LCCs are taxed at a lower rate than cigarettes, are subject to fewer regulations and marketing restrictions, can be purchased in small pack sizes, and are exempt from flavor bans that apply to cigarettes.

In May 2016, the Food and Drug Administration (FDA) required text-only warnings on LCC packs, rotating among six statements. Research on cigarettes suggests warnings on packs should have multiple rotating sets, contain images illustrating the negative health effects associated with LCC use, and be large. (World Health Organization, 2008; Hammond, 2011; Noar, 2016) However, the evidence for cigarette warning labels cannot adequately inform implementation of improved LCC warnings for four reasons: 1) The FDA proposed cigar warnings differ from existing cigarette warnings; 2) there is no evidence on the effectiveness of the FDA proposed cigar warnings (i.e., behavioral intentions or outcomes)(Richardson, 2013; Sterling, 2013; Glasser, 2017) or evidence on efforts that might improve LCC warnings (i.e., images, larger warning size, removal of LCC flavor descriptors on packaging); 3) Courts have ruled that one type of effective tobacco warning (i.e., for cigarettes) cannot be used to justify other types of tobacco warnings, such as those for LCCs; (R.J. Reynolds v. FDA, 2012) and 4) LCC users have different demographic and consumption profiles than cigarette users (i.e., LCC users include a higher proportion of young adults (SAMHSA, 2017), and African Americans, (Nyman, 2016; SAMHSA, 2017), and LCCs are used on fewer days per month)(Nyman, 2016; Jamal, 2018), which should be taken into account when developing improved warnings.

Gaps exist in understanding which LCC warning characteristics (i.e., content, format, size) are most influential in reducing LCC use, and how additional LCC policies, such as removal of flavor descriptors on packaging, influence the impact of LCC warnings. Our project will provide new data to fill these evidence gaps.

Our research on LCC warnings has found that the health effects included in warnings are the most important aspect of warning the warning statement text, and including multiple warnings can lead to stronger warnings, (Jarman, 2021) that that images paired with our warning statements that depict the internal harm or both internal and external harm of smoking LCCs were more effective. (Clark, 2022) In a 2x2 experiment to assess whether warning type (warning statement + image vs. warning statement only) and warning size (30% vs. 50%) were associated with perceived message effectiveness (PME), we found that the warnings that included images were higher in terms of PME than the warnings that were text-only, and that warning size were similar in terms of PME. (Goldstein, 2023)

Given the lack of research on LCC product warnings, our overarching goal is assess whether LCC warnings developed by the study team are more effective than the currently implemented health warnings on LCC products. Given this goal, the choice of comparators are: 1) Newly developed warnings (the six most effective warnings developed by the study team), 2) FDA proposed text-only warnings or 3) No warnings (control condition) in which participants will not see warnings.

Objectives and Hypotheses

Objectives

The proposed study will fill critical gaps regarding which characteristics make LCC warning most effective and provide needed evidence on how LCC warnings influence LCC behavioral intentions. Our overarching goal is to develop effective LCC warnings that reduce cancer and other health risks.

Hypotheses

- Newly developed warnings with images will increase LCC quit intentions more than FDA proposed text-only warnings and more than the control condition in which participants do not see packs or LCC warnings
- The FDA proposed text-only warnings will increase LCC quit intentions more than the control condition
- The warning conditions combined will increase LCC quit intentions more than the control condition
- Newly developed warnings with images will increase self-reported learning more than FDA proposed text-only warnings

Trial Design

The study is designed to be a parallel group trial, with participants evenly allocated to each study condition, using a superiority framework.

Methods: Participants, Interventions, and Outcomes

Methods Overview

We will conduct a 3-week web-based RCT of U.S. adults who currently use LCCs. In this study, LCC warnings on packs will be electronically presented to participants over time to determine if newly developed LCC warnings increase quit intentions compared to FDA proposed text-only warnings and a control condition (in which participants do not see LCC packs or warnings.) We will apply a daily diary methodology to present LCC warnings on packs to participants over time. Qualtrics will contact, screen, consent and administer the survey. To enroll participants, Qualtrics will screen participants using our inclusion criteria and measures and invite eligible participants to enroll in the study. To collect at least 750 quality completes we anticipate enrolling up to 3,000 people.

At the beginning of the baseline survey (day 0), participants will first consent to participate in the study and then complete a questionnaire about their tobacco use and behaviors (e.g., intentions and quit attempts) and other measures of interest. At the end of the baseline questionnaire, survey software will randomly assign participants to one of the 3 study conditions. The three study conditions are: 1) Newly developed warnings (the six most effective warnings developed by the study team), 2) FDA proposed text-only warnings or 3) No warnings (control condition) in which participants will not see warnings. Participants will be contacted via email each day (at approximately 6am) to invite them to complete the survey for that day of the study protocol.

For subsequent days (days 1-6, 8-13, 15-20) participants will be contacted and asked to complete a daily survey which will assess their previous day use of LCCs, as well as cigarettes and e-cigarettes. During these daily surveys, participants assigned to condition 1 or 2 (i.e., the warning conditions) will view an image of a little cigar and cigarillo package with a warning according to the participant's condition. Participants within each warning condition will view a total of 6 different warnings over the course of 6 days each week, this will be repeated 3 times during the study, resulting in a total of 18 exposures. Participants will be required to view the warning for at least 5 seconds before answering questions.

On days 7 and 14 participants will be asked to complete a slightly longer survey with questions about their LCC behaviors including: number of LCCs used in the past week, butted out because they wanted to smoke less, and forgone, other tobacco use, blunt use, and quit intentions and attempts.

For the post-test on day 21, participants will be asked to complete a longer questionnaire about their current tobacco use and behaviors including current LCC smoking behavior, LCC nicotine dependence, OTP use, LCC and OTP quit intentions, and LCC and OTP quit attempts.

Participant timeline

Potential participants will be invited to complete the screener, those who are eligible will be invited to participate in the study. On Day 0, participants will be asked to complete a baseline survey, then a survey every morning for days 1-6, 8-13, and 15-20 to deliver an LCC warning (stimuli shown only for conditions 1 and 2) and assess previous day behavior. Weekly behavior surveys will be completed on days 7 and 14. There is a final post-test on day 21.

Process:

Study Setting

The study will be conducted with online surveys, so participants can complete the surveys from wherever they are. As part of eligibility criteria, all participants will reside in the United States.

Participants

Eligibility criteria for participation in this study:

- 1. Members of the recruitment panel (we are partnering with a panel provider for recruitment of all participants)
- 2. Agree to provide their honest answers
- 3. Current little cigar and/or cigarillo every day or some day users
- 4. Over 21 years old
- 5. Currently living in US
- 6. Inclusion criteria based on the design of the study:
 - a. Feel comfortable taking a survey in English without help
 - b. Feel comfortable taking an online survey without help
 - c. Have an email address that they check regularly
 - d. Have access to the internet at work or home
 - e. Able to read and respond to surveys delivered to their email
 - f. Able to complete 2 surveys that take approximately 20 minutes
 - g. Able to complete a 5 minute survey each day for 20 days
- 7. Inclusion criteria based on verifying real participants:
 - a. Able to verify they are not a bot using CAPTCHA
 - b. Able to answer a simple, random math question

Interventions

Experimental Conditions

- 1. Newly developed warnings: the six most effective warnings developed in Aim 1 at 30% size
- 2. FDA proposed text-only warnings: the six currently proposed warnings at 30% size
- 3. Control group: a control condition in which participants will not see warnings, but will be asked to complete daily surveys on previous-day LCC behaviors

Warning Stimuli

The stimuli for conditions 1 and 2 will vary based on the day of the protocol. The packages that the study warning labels will be shown on is standardized, warning labels will be shown on both a cigarillo and little cigar package (see table below: Stimuli Shown by Condition), and the packages will be purple and branded with the fictitious name "Brentfield" which has successfully been used in prior research to minimize the influence of brand loyalty and pre-existing brand perceptions. The warnings will be shown on the bottom 30% of the front of the package. Warning text for both warning conditions will be centered and the marker word "WARNING" was placed on a separate line. In accordance with FDA guidelines, warning text will be displayed in an arial bold type font. Across all warnings, the font in little cigar warnings was size 12 and in cigarillo packages, the font was size 14. (FDA, 2020)

For all warning conditions, LCC packages will be centered and placed on either a plain white background or light grey, blurred background. When present, background images will be consistent with locations where LCCs could be purchased (i.e., at a counter or in a grocery store, or blank). The background is used to give context to the stimuli that may help participants focus on it and give a more real world feeling.

Stimuli Shown by Condition:

Condition	Six Warning Messages Presented	Example LCC pa	Example LCC package depicted on each background		
		Transparent (White)	Grocery Store	Cigar Counter	
Newly developed warnings (Condition 1)	WARNING: Cigar smoking causes pharyngeal and throat cancer.	Wenthery CEALLEAN Wenthery (HERECHAN 2 2 30 Commonting states Commonting states Commonting states Commonting states Commonting states Commonting states	Committee (Committee)	Windling Continue Con	
	WARNING: Cigar smoking causes stroke and blood clots.	CALIFICATION COLUMN TO THE CO	Committee of the control of the cont	COLUMN DESCRIPTION OF THE PROPERTY OF THE PROP	
	WARNING: Cigar smoking causes colon cancer.	Commence of the control of the contr	Commence of the control of the contr	Commission contents of the con	

	WARNING: Cigar smoking causes bladder cancer and blood in urine.	Green Maries West Miles West	STATISTICAL STATIS	granticity cuantics granticity cuantics granticity cuantics granticity cuantics granticity cuantics grantics cuantics cu
	WARNING: Cigar smoking causes esophageal cancer.	Wenthery CENTRAL WENTHERY CONTROL STORY CONTROL	Grant Incl. Grant	GENERAL CONTROL CONTRO
	WARNING: Cigar smoking causes lung cancer and lung disease.	Greatifiely CGARTICO BIGHT GIGHTS ALTRICO ALT	GEARTICAL STREET OF THE STREET	GENERAL SECTION OF THE PROPERTY OF THE PROPERT
FDA proposed text-only warnings (Condition 2)	WARNING: Cigar smoking can cause cancers of the mouth and throat, even if you do not inhale.	WANNIEG WANNIEG Cigar amoting can conver of the convert of the c	WestMin/I/ CITATITUS WANDAMING COpy mending can be seen conserved and front for month and for	CONTROL CONTRO
	WARNING: Cigar smoking can cause lung cancer and heart disease.	WARNING: Class manking can cases lung cancer and heart disease.	Countries Constitution Constitu	Cigar anothing cane case hard disease.
	WARNING: Cigars are not a safe alternative to cigarettes.	WASHING: Coperation WASHING: Coperation Output Outp	Westificity CEASITION WESTIFICATION WESTIFICATION WASHING COgness or old a shall administer to squareds to objection.	WARNING: Cape are not a safe disparence. To cigarente.

	WARNING: Tobacco smoke increases the risk of lung cancer and heart disease, even in nonsmokers.	WORKER CONSTRUCT WORKER WORKER Telescon smoke Increases for fac for lang cancer and heart disease, even in nonemakers.	Tables on the big second of the second of th	TOTALING WINNEY Todacco mode successes the risk of larg career and heart disease, even in monancies.
	WARNING: Cigar use while pregnant can harm you and your baby.	WARNING: Cigar use while prognant can harm you and your bally.	WEATHER COMMITTEE COMMITTE	COUNTRY COUNTR
	WARNING: This product contains nicotine. Nicotine is an addictive chemical.	Wenthely GOALILOS Wenthely CITTLE GOALS WANNE Wannel Wanne	granticly continues addition demans.	CONTINUES WASHING WASHING This product contains shorters when the shorters is an additive channel.
No stimuli: Control (Condition 3)	For condition 3, the control, participants were not presented any stimuli.	N/A	N/A	N/A

Stimuli Order

Day	Message	Condition 1	Condition 2	Background
Day 1	Α	Throat	Mouth	Plain
Day 2	В	Lung	Heart	Grocery
Day 3	F	Stroke	Nicotine	Counter
Day 4	С	Colon	Unsafe	Plain
Day 5	E	Bladder	Baby	Counter
Day 6	D	Esoph	SHS	Grocery
Day 8	В	Lung	Heart	Plain
Day 9	С	Colon	Unsafe	Grocery
Day 10	Α	Throat	Mouth	Counter
Day 11	D	Esoph	SHS	Counter
Day 12	F	Stroke	Nicotine	Grocery
Day 13	E	Bladder	Baby	Plain
Day 15	С	Colon	Unsafe	Counter
Day 16	D	Esoph	SHS	Plain
Day 17	В	Lung	Heart	Counter
Day 18	E	Bladder	Baby	Grocery
Day 19	Α	Throat	Mouth	Grocery
Day 20	F	Stroke	Nicotine	Plain

Condition 3 does not have a stimuli order because that condition does not see packages or warnings, their daily surveys are only to assess behavior

Message Order (based on Latin Square design)

- In week 1, participants see the following message order: A-B-F-C-E-D (sequence 1)
- In week 2, participants see the following message order: B-C-A-D-F-E (sequence 2)
- In week 3, participants see the following message order: C-D-B-E-A-F (sequence 3)

Message by Condition:

Message Letter	Condition 1: Text + Image Warning	Condition 2: FDA Text Only Warning
Α	WARNING: Cigar smoking causes	WARNING: Cigar smoking can cause cancers
	pharyngeal and throat cancer.	of the mouth and throat, even if you do not
	(Throat1)	inhale.
		(Mouth2)
В	WARNING: Cigar smoking causes	WARNING: Cigar smoking can cause lung
	lung cancer and lung disease.	cancer and heart disease.
	(Lung1)	(Heart2)
С	WARNING: Cigar smoking causes	WARNING: Cigars are not a safe alternative
	colon cancer.	to cigarettes.
	(Colon1)	(Unsafe2)
D	WARNING: Cigar smoking causes	WARNING: Tobacco smoke increases the risk
	esophageal cancer.	of lung cancer and heart disease, even in
	(Esoph1)	nonsmokers.
		(SHS2)
E	WARNING: Cigar smoking causes	WARNING: Cigar use while pregnant can
	bladder cancer and blood in urine.	harm you and your baby.
	(Bladder1)	(Baby2)

Message Letter	Condition 1: Text + Image Warning	Condition 2: FDA Text Only Warning
F	WARNING: Cigar smoking causes	WARNING: This product contains nicotine.
	stroke and blood clots.	Nicotine is an addictive chemical.
	(Stroke1)	(Nicotine2)

Background Order (based on Latin Square Design)

We will have 3 background options (A=Plain, B=Counter, C=Grocery), they will be counterbalanced in order based on day

- Message A will have background sequence: A, B, C (Sequence 1)
- Message B will have background sequence: C, A, B (Sequence 3)
- Message C will have background sequence: A, C, B (Sequence 2)
- Message D will have background sequence: C, B, A (Sequence 4)
- Message E will have background sequence: B, A, C (Sequence 6)
- Message F will have background sequence: B, C, A (Sequence 5)

Additional intervention details

Participants can withdraw from the study if they choose by no longer responding to the survey links and may withdraw their data by contacting the UNC study team.

Multiple strategies have been implemented to maximize adherence to the trial protocol, including reaching out to participants via email with invitations and reminders each day, compensating them based on completion of the most important questionnaires.

There is no relevant concomitant care or interventions that are permitted or prohibited during the trial.

Outcomes

[figure not shown]
Primary

- LCC guit intentions at post test (day 21)
 - Average quit intention score measured by survey, Quit intention measured with 3 questions, the final
 quit intention score is a mean of the response to the 3 questions, on a scale of 1 to 4, where 1 indicates
 low intention to quit, and 4 indicates a high intention to quit.

Secondary

- Number of LCCs smoked in past day (each day)
 - Measured daily by survey
- Number of days smoked LCCs in past week (days 7, 14, and 21)
 - Measured weekly by survey
- Number of LCCs smoked in the past week (days 7, 14, and 21)
 - Measured weekly by survey
- Butting out LCCs (days 7, 14, and 21)
 - Measured weekly by survey
- Forgoing LCCs (days 7, 14, and 21)
 - Measured weekly by survey
- LCC quit attempts (days 7, 14, and 21)
 - Measured weekly by survey
- LCC quit intentions (days 7 and 14)

- Average quit intention score measured by survey, Quit intention measured with 3 questions, the final
 quit intention score is a mean of the response to the 3 questions, on a scale of 1 to 4, where 1 indicates
 low intention to quit, and 4 indicates a high intention to quit.
- Self-reported learning (day 21) (only conditions 1 and 2)
 - Measured by survey. Self-reported learning measured with one item on a 1 to 5 scale, where 1 indicates no learning, and 5 indicates a great deal of learning from the warnings in the study.

Sample Size

The sample size is based on quit intentions effect sizes from an RCT comparing graphic cigarette warnings to text only warnings (Brewer, 2016). Based on the effect size observed in that study, we would have 80% power at α =0.05 to detect a small change in differences between our groups (f=0.12).

Recruitment

We are working with Qualtrics research services to conduct this study and enroll participants from one of the panel providers that they work with. Qualtrics has access to high quality research panels across the US. They are able to leverage these panels to provide timely and reliable data collection to UNC and other research universities. We have high confidence that Qualtrics will be able to meet our recruitment goals.

Compensation Plan

Qualtrics will manage participant incentives. Participants in studies conducted by Qualtrics receive an incentive based on the length of the survey and their specific profile. The types of rewards vary and may include cash, airline miles, gift cards, redeemable points, sweepstakes entrance and vouchers. Participants who complete only the screening survey will receive a small incentive. For this study, participants who complete the baseline, 6 of the daily message surveys, at least one of the weekly surveys (day 7 or day 14), and day 21 will receive an incentive. Participants who complete only a few of the surveys but do not satisfy the criteria above will not receive an incentive.

Methods: Assignment of interventions

Allocation and Blinding

Participants will not be informed specifically about the possible interventions that they may be assigned to. Researchers will not be blinded to the condition that participants had been assigned to, however all outcome measures will be assessed via online survey. At the end of the baseline survey, survey software will randomly assign participants to one of the three study arms. Participants will have an equal chance of being randomized to each study arm.

Methods: Data collection management, and analysis

Data collection methods

Data collection will be conducted using Qualtrics web survey platform, questionnaires and references for measures can be found in the study measures document. Where possible, the measures used are previously developed and validated measures. Multiple strategies have been implemented to maximize adherence to the trial protocol, including reaching out to participants via email with invitations and reminders each day, and compensating them based on completion of the most important questionnaires.

Screener

Qualtrics will use invite potential participants to complete the screening survey and people who are eligible will be invited to complete the baseline survey. The screener is used to assess participant eligibility and collect demographic data.

Baseline Survey: Day 0

- Eligible participants will be invited to participate in the study and complete the baseline survey to enroll
- The first part of the baseline survey will be a consent form with an agreement to participate in the study
- The baseline survey contains baseline tobacco use questions (e.g., motivation to quit, previous year LCC quit attempts, nicotine dependence, etc.).

 At the end of the baseline questionnaire, survey software will randomly assign participants to one of the 3 study conditions

Daily Surveys: Days 1-6, 8-13, and 15-20

- There are 18 daily surveys, which align with each participant's condition. Participants in conditions 1 and 2 will be shown stimuli (in accordance with their assigned condition) and condition 3 will not see any stimuli. Participants will stay in their condition throughout the study. Depending on the day, participants will see a different message
- Daily surveys will be sent out at 6am EST and will close at 2am EST (gives west coast until 11pm to complete surveys). There will be a reminder email sent in the afternoon.

Weekly Surveys: Days 7, 14

- Weekly behavior surveys will include questions about LCC behaviors including: number of LCCs used in the past
 week, butted out because they wanted to smoke less, and forgone), other tobacco use (OTP), blunt use, and quit
 intentions and attempts.)
- The weekly surveys will be sent out at 6am EST and will close 48 hours later. There will be a reminder email sent in the afternoon, and the next day.

Post-Test Survey: Day 21

- For the post-test on day 21, participants will be asked to complete a longer questionnaire about their current tobacco use and behaviors including current LCC smoking behavior, LCC nicotine dependence, OTP use, LCC and OTP quit intentions, and LCC and OTP quit attempts.
- Participants in conditions 1 and 2 will be asked recognition questions to assess whether they can recognize warnings shown to them in their condition
- Participants will also be asked about their study experience
- The post-test surveys will be sent out at 6am EST and will close 48 hours later. There will be a reminder email sent in the afternoon, and the next day.

Data Management

Data management will be conducted by the study team. Multiple processes have been implemented to ensure high data quality, including internal pilots to test the protocol and ensure that data collection instruments are working properly, and ongoing data monitoring will be conducted during data collection to ensure that any issues with data quality are caught early and fixed. A pilot of the protocol with actual participants will be conducted before the full study is launched and participants will be asked about their experience in the study at the end of the pilot to further ensure that the protocol is working as intended and ensure a high quality data collection.

Statistical Methods

We will analyze the data using intention-to-treat analyses. Our primary outcome is LCC quit intention at post-test. We will model LCC quit intentions with message condition (warnings with images, FDA proposed text-only warnings, and a no warning control) as the between-participant predictor.

Analysis methods will depend on the time point that the outcome was measured. Post-test measures will be analyzed differently than repeated measures from the daily survey and weekly surveys, as outlined below. All models will include a categorical indicator of day to control for the durable linear effect of time.

Analysis methods for post-test measures will use linear regression for continuous outcomes, including the primary outcome of quit intentions, and logistic regression for dichotomous outcomes. Imputation will be used so that all participants who were randomized to an intervention and completed at least one daily survey will be included in the analysis, consistent with intention to treat practices.

Secondary models will examine differences between groups for items measured multiple times in either daily or weekly surveys (ex., LCC behavior measures). For these models, we will use linear mixed modeling to account for the repeated measure design. Mixed models are appropriate to use and robust to missing data, so we will be able to include everyone who completed at least 1 daily questionnaire, consistent with intention to treat practices.

Secondary models will also be run for the primary outcome as well as secondary outcomes that include the number of daily surveys completed (This is a measure that is equivalent to the dose of the stimuli for the active condition and also applies to the control condition)

LCC behavior is collected separately for cigarillos and little cigars and will be combined in the main analyses for these outcomes (ex. Number of cigarillos in past day and number of little cigars in past day combined for number of LCCs in past day). We also plan to run separate analyses for cigarillo behavior and little cigar behavior.

Additional information about the statistical analysis can be found in the Statistical Analysis Plan.

Methods: Monitoring

To ensure maximum protection of human subjects, we submitted our research project information to the School of Medicine Data Safety and Monitoring Board at the University of North Carolina at Chapel Hill and asked them to make the final decision regarding risk to participants and whether or not our studies should receive their supervision. A representative of the board agreed that given that the study involves a low risk behavioral intervention in a healthy population, that oversight by the board was not necessary.

Adverse events are not expected in this trial due to the minimal risks to participants, and no threat to participant health, so plans for collecting, assessing and reporting adverse events are not necessary.

We have no plans for auditing trial conduct.

Ethics and dissemination

This trial was granted an exemption by UNC's IRB under IRB # 22-2531.

All protocol changes will be communicated to the study team, and any change in participant interaction will be approved by UNC's IRB. Protocol changes will be tracked in an appendix table with new versions after initial approval including the date, version number, and a summary of changes.

Consent

Consent will be collected electronically as part of the baseline survey at the beginning of the study. At the beginning of the baseline survey, participants will view the consent form with an agreement to participate in the study. Participants will only be able to proceed with the study if they agree to participate in the study.

Confidentiality

We will take the following steps to minimize the risk to a breach of confidentiality via unauthorized access, use, disclosure, modification, loss or theft of participants' information: We will use and enforce appropriate security measures including physical, technical and administrative safeguards. Data will be stored on a university secure server that is password accessed and is only accessible to key research personnel. All study personnel are required to have valid training on ethics of research on human subjects and to complete confidentiality certification procedures upon employment. The research team will not have access to personal identifying information.

This study proposes research that has been determined to include Security Level 1 data security requirements. The PI has agreed to accept responsibility for managing these risks appropriately in consultation with departmental and/or

campus security personnel. The Data Security Requirements addendum can be reviewed here: https://guides.lib.unc.edu/datasecurity/irbis

Declaration of Interests

The study team declare that they have no competing interests.

Access to data

We will make data collection instruments available for public use after data collection and analyses are complete. On request, we will also make data sets available, stripped of individual identifiers, following publication of the relevant study's main findings. We may submit deidentified data collected in this study to a data repository, such as UNC Odum Institute's Dataverse (https://dataverse.unc.edu/dataverse/unc) to make our deidentified data publicly available. As part of submitting the data to a repository we will provide basic information about how the data was collected and upload a deidentified dataset to the repository.

Ancillary and post-trial care

This trial presents no more than minimal risk to participants, does not collect data on harms to participants or assess interim data during the trial. There is no need for ancillary or post-trail care.

Dissemination Plan

The study team plans to disseminate study findings via conference presentation and peer reviewed manuscripts in scientific journals. The study team will also share findings via ClinicalTrials.gov registration. We will follow authorship guidelines depending on the journal to which manuscripts are submitted. There are currently no plans to make a participant level dataset public.

References

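### The Day-1 past-day report describes Day 0, before any warning, and no stated rule keeps it out of the daily LCC count model, so the averaged arm effect shrinks by about 5%, and by more with early dropout

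*Combined protocol and SAP*

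**What the plan says.** Methods Overview sets the order of events. On Day 0, "At the end of the baseline questionnaire, survey software will randomly assign participants to one of the 3 study conditions", and no warning is scheduled that day. On the daily-survey days participants are "asked to complete a daily survey which will assess their previous day use of LCCs". Participant timeline confirms that the same surveys carry the intervention: a baseline survey, "then a survey every morning for days 1-6, 8-13, and 15-20 to deliver an LCC warning". The Stimuli Order table begins at Day 1.

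The secondary list under Outcomes includes "Number of LCCs smoked in past day (each day").

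Under Statistical Methods, repeated outcomes are analysed by linear mixed model. On time, "All models will include a categorical indicator of day to control for the durable linear effect of time". On the analysis set, "we will be able to include everyone who completed at least 1 daily questionnaire". For the two product types, "We also plan to run separate analyses for cigarillo behavior and little cigar behavior".

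Statistical Methods refers to a Statistical Analysis Plan for more detail, but no separate SAP section is in the text supplied.

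**The concern.** A morning survey that both shows the day's warning and asks about yesterday has outcome and exposure one day out of step. The Day-2 report is the first that can reflect a warning. The Day-1 report covers Day 0, so its true arm difference is zero by design.

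If that record enters the outcome series, an arm effect averaged over days includes one day on which no effect was possible. The categorical day term does not correct this. It is common to all arms, so it absorbs a shared Day-1 level but not the missing arm difference. Someone whose only past-day report is Day 1 also qualifies for the model while contributing no post-exposure data.

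At stake are the estimate and power for one secondary outcome and for its separate cigarillo and little-cigar versions. The trial is framed as a superiority comparison, so a bias toward no difference works against finding a real effect.

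**Working it through.** The documents give no figure for this dilution, so there is none to reproduce.

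**Inputs from the documents**
- 18 daily surveys, Days 1-6, 8-13 and 15-20 (Methods Overview; Daily Surveys).
- Past-day items also sit in the Weekly Behavior Assessment (Appendix B). That adds Days 7, 14 and 21, giving up to 21 reports after baseline.
- The analysis set is anyone with at least one daily questionnaire (Statistical Methods).
- At least 750 quality completes from up to 3,000 enrolled (Methods Overview). This is not stated to be a retention figure.

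**Complete diaries.** With T reports per person and zero effect in the first, the averaged arm effect is (T-1)/T of the effect over the other days. The shrinkage is 1/T, whatever the shape of the effect over later days.
- T = 18: 1/18 = 5.6%.
- T = 21: 1/21 = 4.8%.
- If the Day 0 past-day items were also counted as outcomes, 2/22 = 9.1%.

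Missed days scattered evenly over the diary leave 1/T unchanged.

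**Dropout.** Assumptions, none of them in the documents: condition plus categorical day plus a random intercept with intraclass correlation ρ; the same dropout in each arm; zero effect in the Day-1 report and a constant effect afterwards. Let p_n be the share of people with n consecutive records from Day 1. Then

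shrinkage = Σ[p_n / (1+(n-1)ρ)] / Σ[n·p_n / (1+(n-1)ρ)].

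Under a constant hazard with retention r to the last record, the share still giving record k is r^((k-1)/(T-1)). For ρ from 0.2 to 0.8:

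| Retention r | T = 18 | T = 21 |
|---|---|---|
| 100% | 5.6% | 4.8% |
| 75% | 7.5-9.2% | 6.6-8.0% |
| 50% | 10.3-13.8% | 9.0-12.2% |
| 25% | 14.7-20.7% | 13.1-18.5% |

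The 25% row is 750/3,000 read as retention, which is only an illustration. Generalised least squares with day fixed effects gave the same values to four decimals.

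Dropout raises the shrinkage above Day 1's share of records, because a random-intercept model gives people with few records more weight per record. At r = 25% and T = 18, Day 1 makes up 10.2% of records, while the shrinkage is 14.7-20.7%. In that case 1 - 0.25^(1/17) = 7.8% of people have the Day-1 report only.

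**Other dropout patterns.** Dropout spread evenly over the study, with ρ from 0 to 0.9 and either T, gives 5.4-9.0% at 75% completers, 6.3-12.6% at 50% and 7.6-16.1% at 25%. If all dropout falls in the first week, the result is 8.2-22.5% at 50% and 12.7-31.1% at 25%.

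**Power.** For a contrast that would have 80% power (two-sided 0.05), power after shrinkage s is Φ((1-s)(1.960+0.842) - 1.960). This gives about 76% at s = 4.8% and 75% at s = 5.6%.

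**The case against.** The strongest objection is that the model is not fully specified. Statistical Methods points to a Statistical Analysis Plan, which could exclude Day 1, add a condition-by-day term or name a baseline covariate. The outcome list may describe collection rather than which records enter the model, and no document names an averaged arm contrast. This stands as a condition: the entry of the Day-1 report is inferred from the outcome being listed for each day, and the averaged contrast is assumed. But nothing in the supplied text removes the record, and stating the rule settles the matter either way.

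The effect is also modest. The only figures free of a dropout assumption are 4.8-5.6%. None of the listed hypotheses concerns daily LCC count. The larger figures rest on chosen patterns, and the incentive rule (six daily surveys, one weekly survey and Day 21) permits scattered completion, under which 1/T applies. All of this is true and limits the weight of the point; it does not remove the dilution.

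Two points bear on the boundary. If the warning precedes the past-day items, Day-1 reporting, though not Day 0 smoking, could be influenced. And the Day-1 survey stays open until 2am EST, so for late responders the Day-2 report describes a day that was largely unexposed. Starting at Day 2 is therefore not a perfectly clean cut, but Day 2 is at most partly unexposed, whereas Day 1 is wholly so.

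Finally, dropping Day 1 narrows the stated analysis set. The people lost carry no post-exposure information on this outcome.

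**Conclusion.** The concern holds. On the stated schedule the Day-1 past-day report describes a day before any warning, and nothing in the supplied text keeps it out of the arm contrast. With complete diaries the averaged effect on daily LCC count shrinks by 5.6% (18 reports) or 4.8% (21 reports). Early dropout raises this by an amount that depends on its pattern; no retention figure is given, so the dropout ranges are illustrative.

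The conclusion rests on two readings: that the Day-1 report is part of the outcome series, and that the reported effect is averaged over days. The bias is toward no difference and does not inflate type I error. It is confined to past-day LCC count and its two product-specific versions; quit intentions at Day 21 are unaffected. The change is worth making because it is cheap, but the trial's main conclusion does not depend on it.

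**What to change.** State in the SAP that the past-day outcome series (LCC, cigarillo and little cigar) begins with the Day-2 report. Adjust these models for LCC use collected in the Day 0 survey before randomisation: the past-week number smoked from the Weekly Behavior Assessment, plus its past-day items if wanted. If the full SAP already excludes the Day-1 report, confirming that is enough.

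Use the Day-1 report as a further covariate only if its past-day items are confirmed to be answered before the first warning is displayed. The documents do not settle this. Methods Overview says "Participants will be required to view the warning for at least 5 seconds before answering questions", while Appendix B lists the past-day items ahead of the stimuli without saying that this is the display order.

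The cost is one or two sentences and no new data. With complete diaries and within-person correlation of 0.3 to 0.7, dropping one report raises the variance of a person's mean by 0.1% to 0.7%. Participants with no past-day report after Day 1 leave these models only; report their number by arm. The at-least-one-questionnaire rule stays as it is for other outcomes.
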